4.3. Type and Number of Subjects

A total of 528 subjects are required including a total of 12 centres (6 centres per group) and around 44 asthma subjects per centre.

4.4. Design Justification

- We design our study to address the effectiveness of the intervention if implemented in a system without other enhanced healthcare options; we therefore use a usual care control group.
- Randomization by individual subjects may result the contamination due to the same investigator looking after both intervention and control group. Randomization by clusters (i.e., study centre) will reduce such bias.

4.5. Benefit:Risk Assessment

The following section outlines the risk assessment and mitigation strategy for this protocol:

4.5.1. Risk Assessment

Potential Risk of Clinical Significance	Summary of Data/Rationale for Risk	Mitigation Strategy
Study Procedures		
Patients' inappropriate understanding on ACT questionnaire	ACT is consisted of five questions, which each have a five-point rating scale and relate to the past month. It is not an objective tool.	Once a subject is enrolled into the study, the investigator is responsible for training the subject to understand and use the ACT.

4.5.2. Benefit Assessment

Usage of the ACT is beneficial for patients. The ACT as an easy and patient-friendly tool for asthma control assessment has been fully validated and used in interventional studies and routine clinical practice in many countries. The ACT empowers patients to take charge of their condition and work in partnership with their physicians, which could facilitate the achievement of guideline-defined asthma control.

4.5.3. Overall Benefit: Risk Conclusion

Taking into account the measures taken to minimize risk to subjects participating in this study, the potential risks identified in association with inappropriate understanding on ACT questionnaire are justified by the anticipated benefits that may be afforded to subjects with asthma.

5. SELECTION OF STUDY POPULATION AND WITHDRAWAL CRITERIA

Deviations from inclusion and exclusion criteria are not allowed because they can potentially jeopardize the scientific integrity of the study, regulatory acceptability or subject safety. Therefore, adherence to the criteria as specified in the protocol is essential.

5.1. Inclusion Criteria

Inclusion criteria for study centre (clusters):

A study centre (cluster) will be eligible for inclusion in this study only if all of the following criteria apply:

1. General practice;
2. Located in Shanghai;
3. Providing asthma care.

Inclusion criteria for subjects at Visit 0:

A subject will be eligible for inclusion in this study only if all of the following criteria apply:

4. Age: 18 to 70 years inclusive;
5. Gender: Male or Female;
6. Documented clinical history of asthma for at least 6 months prior to Visit 0;
7. At Visit 0, a demonstrable reversible increase in FEV1 of at least 12% (and ≥ 200 mL), 15 minutes after inhaling a short-acting bronchodilator or; at any time in the last 2 years documentary evidence of a reversible increase in FEV1 of at least 12% (and ≥ 200 mL) 15 mins after inhaling a short-acting bronchodilator; or demonstrable reversible increase in morning PEF of at least 15% (and ≥ 200 mL) either spontaneously or after inhalation of a short-acting bronchodilator;
8. History of using inhaled corticosteroids (ICS) alone or combined with an inhaled long-acting β_2 agonist (LABA) treatment within 1 year prior to Visit 0;
9. Subjects must have an ACT score < 20 at Visit 0;
10. Subject must have been able to read, comprehend, and record information in Chinese;
11. A signed and dated written informed consent must be obtained from the subject prior to study participation.

5.2. Exclusion Criteria

A subject will not be eligible for inclusion in this study if any of the following criteria apply:

1. History of Life-threatening asthma: Defined for this protocol as an asthma episode that required intubation and/or was associated with hypercapnea, respiratory arrest or hypoxic seizures within the last 6 months before Visit 0.
2. Subjects having severe and unstable asthma, with ACT score <12 at Visit 0, history of repeated severe exacerbations (3/year) and/or a severe exacerbation in the previous 6 weeks before Visit 0.
3. A current evidence of clinically significant uncontrolled medical condition or disease (e.g., psychological disorders, mental deficiency, severe hepatic and renal dysfunction, malignancy);
4. Current smoker or ex-smoker with a more than 10 pack-year history of smoking;
5. Current clinically significant respiratory diseases other than asthma, (e.g lung cancer, lung fibrosis, sarcoidosis, tuberculosis, chronic obstructive pulmonary disease [COPD]);
6. History of alcohol or medication abuse;
7. History of upper or lower respiratory tract infection within 4 weeks prior to Visit 0;
8. Enrolled in an asthma clinic or outpatient service in the past 12 months that provides comprehensive asthma management;
9. Subjects with a history of adverse reaction including immediate or delayed hypersensitivity to any intranasal, inhaled, or systemic corticosteroid and LABA therapy and to components of the inhalation powder (e.g., lactose) at Visit 0. In addition, subjects with a history of severe milk protein allergy that, in the opinion of the Investigator, contraindicates the subject's participation will also be excluded.
10. Females who are currently pregnant and lactating;
11. Subjects who have received any of the following medications in the 6 weeks preceding visit 0: oral/parenteral corticosteroids, oral β 2-agonists or slow-release

bronchodilators, sodium cromoglycate or nedocromil sodium, ketotifen, anticholinergics, and anti-IgE treatment;

12. Subjects who comply poorly with asthma treatment in the opinion of the investigator/inability or unwillingness to take asthma medication (non-compliance), follow directions or unable to complete a written paper daily record card and self-rating questionnaires;
13. Concurrently participating in another clinical study in which the subject is or will be exposed to an investigational or a non-investigational medication or device, or has participated in a clinical trial and has received an investigational product within 30 days, 5 half-lives or twice the duration of the biological effect of the investigational product (whichever is longer).
14. Subjects with contraindications to any asthma medications they will be taking during the study period, or whom should be excluded on account of the special warnings and precautions within the label of the asthma medication they are to be treated with during the study period.
15. Affiliation with Investigator Site: Is an investigator, sub-investigator, study coordinator, employee of a participating investigator or study site, or immediate family member of the afore mentioned that is involved in this study.
16. Subjects who plan to move away from the geographical area where the study is being conducted during the study.

5.3. Withdrawal/Stopping Criteria

The primary reason for the subject discontinuing from the study will be recorded in the Case Record Form. The investigator must determine the primary reason for discontinuation. The end of study/early discontinuation procedures must be performed at the time of discontinuation from the clinical study.

The subject **must** be discontinued from the study for any of the following reasons:

1. A subject is significantly non-compliant with treatment or the requirements of the protocol;
2. Lost to follow up;
3. Subject's decision not to participate any further (withdrawal of consent);
4. In the investigator's opinion, it is in the subject's best interest;
5. Subjects experience a protocol-defined asthma exacerbation;
6. The study is terminated by the Sponsor or designee;
7. Pregnancy (Subject should notify investigator immediately on becoming pregnant).

A subject may withdraw from study treatment at any time at his/her own request, or may be withdrawn at any time at the discretion of the investigator for safety, behavioural or administrative reasons.

The reason(s) for subjects not completing the study will be recorded in the Case Report Form (CRF), and that the investigator must document, if applicable, the reason (if specified by the subject) for withdrawal of consent. The end of study/early discontinuation procedures must be performed at the time of discontinuation from the clinical study.

The following actions must be taken in relation to a subject who fails to attend the clinic for a required study visit:

- The site must attempt to contact the subject and re-schedule the missed visit as soon as possible.
- The site must counsel the subject on the importance of maintaining the assigned visit schedule and ascertain whether or not the subject wishes to and/or should continue in the study based on previous non-compliance.
- In cases where the subject is deemed 'lost to follow up', the investigator or designee must make every effort to regain contact with the subject (where possible, 3 telephone calls and if necessary a certified letter to the subject's last

known mailing address or local equivalent methods). These contact attempts should be documented in the subject's medical record.

- Should the subject continue to be unreachable, only then will he/she be considered to have withdrawn from the study with a primary reason of "Lost to Follow-up".

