6. STUDY TREATMENT

6.1. Treatment Assignment

The study is a trial with the study centre as the unit of randomization. Computer generated randomization schedule for centres will be provided by GlaxoSmithKline (GSK) or its designee. Once a randomization number has been assigned, it is not re-assigned. Each centre will be randomized to either ACT guided treatment group or control group (usual care group). The randomization will be stratified according to the Tier of the hospitals (Tier 3 vs. Tier 2). Assignment to a treatment will not occur, as no treatment intervention is provided for this study. Each centre will be asked to recruit 44 consecutive patients with asthma attending the practice. For the subjects who are recruited in the ACT centres, they will be treated based on the ACT score. For subjects who are recruited in the control centres, they will be treated based on doctor's subjective judgment.

The subject number will be documented in the subject's clinic notes and in the CRF.

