9.3.1. Analysis Populations

Three populations are defined for this study.

- Intent-to-Treat (ITT) Population: all subjects who signed informed consent form, were randomised and who had at least one post-baseline assessment. The ITT population will be the primary population of interest.
- Per Protocol (PP) Population: all subjects in the ITT population with no major protocol deviations and with $\geq 80\%$ treatment compliance and diary compliance. The PP population will not be analyzed if this population comprises more than 95% or

less than 50% of the ITT population. Only the primary efficacy variables will be analyzed using the PP population.

- Safety Population: all subjects who are enrolled into the study and who have at least one DRC assessment.

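### Mandatory study discontinuation for undefined significant non-compliance ends outcome collection early in an effectiveness trial, with a risk of selective loss of unknown direction and size

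*Protocol*

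**What the plan says.** Protocol section 5.3 states that a subject must "be discontinued from the study for any of the following reasons", and the first reason is: "A subject is significantly non-compliant with treatment or the requirements of the protocol". The word *significantly* is not defined. Sites verify withdrawal criteria and assess compliance at Visits 1 to 6 (section 7.1), and the trial is open-label (section 6.2).

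On leaving, one further set of assessments is taken: "The end of study/early discontinuation procedures must be performed at the time of discontinuation from the clinical study". Section 7.1 labels the last column as Visit 6 or early withdrawal; it contains ACT, AQLQ(S), lung function and diary collection. No later contact for outcomes is planned.

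The purpose is stated in section 4.4: "We design our study to address the effectiveness of the intervention if implemented in a system without other enhanced healthcare options". Section 6.1 adds: "Assignment to a treatment will not occur, as no treatment intervention is provided for this study". ITT is the primary population. The Per Protocol population is "all subjects in the ITT population with no major protocol deviations and with" at least 80% treatment compliance and diary compliance (Protocol section 9.3.1; SAP sections 4.2 and 4.3).

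**The concern.** The trial compares two ways of managing asthma under ordinary conditions. How well patients take what they are prescribed belongs to how either strategy performs. The sponsor supplies no drug, so leaving the study withdraws no study product. It ends follow-up under the allocated strategy, after one last visit.

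Removing non-compliant subjects applies a selection that belongs to the Per Protocol analysis to the collection of ITT data, using an unwritten threshold applied by people who know the allocation. The two strategies may also lead to different prescribing: Table 1 of the protocol ties step-up to an ACT of 19 or below, while control centres follow the doctor's judgement. The expected benefit of ACT is partly behavioural: "The ACT empowers patients to take charge of their condition and work in partnership with their physicians". The chance of being judged non-compliant could therefore differ by arm. Outcomes that are never collected cannot be recovered in the analysis.

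**Working it through.** **1. What each analysis keeps for a subject removed under item 1**

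- *FEV1 and AQLQ(S) change* (SAP 7.2.2): only subjects who finish the study, as Visit 6 minus baseline. A completer has attended all visits (Protocol 5.4). Removed subjects drop out, although both measures are taken at the early-withdrawal visit. This is the most direct exposure.
- *Diary symptom and PEF means* (SAP 7.2.2): no imputation; a period mean is missing with fewer than 14 recorded days. Later periods are lost.
- *By-visit GEE and ACT-change MMRM* (SAP 7.1.3): observed visits only. The unweighted GEE needs missingness unrelated to outcome; the MMRM needs it explained by observed data.
- *Primary endpoint* (SAP 7.1.1): a response at any post-baseline ACT counts, among subjects with at least one such ACT. Responses up to and including the early-withdrawal visit are kept; later chances are lost, without imputation (Protocol 9.3.2).
- *Stricter endpoints at Weeks 12, 24 and 16-20-24* (SAP 7.1.3): missing counts as non-response, so removed subjects stay in. This covers the *and* definition only, not the primary *or* definition.

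**2. The plan's own figure**

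Inputs (Protocol 9.2.1): 29% against 44%, ICC 0.01, 35 evaluable subjects in each of 6 centres per arm, two-sided 0.05, 80% power, 20% dropout. Design effect = 1 + (35 − 1) × 0.01 = 1.34. The unadjusted size is 161 per arm (pooled variance) or 158 (unpooled). Totals are 2 × 161 × 1.34 = 431 and 2 × 158 × 1.34 = 423, against 420 stated. Power with 210 per arm is 79.0%. Dropout: 35 / 0.8 = 43.75, so 44 per centre and 528 in all. The plan's figure reproduces. The 20% is one overall rate, not split by arm or reason.

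**3. Primary endpoint, illustration in both directions**

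Subjects removed after a post-baseline ACT remain in the analysis, so the base is 6 × 44 = 264 per arm, with design effect 1 + 43 × 0.01 = 1.43 and effective n = 264 / 1.43 = 184.6. Power = Φ{[d√n − 1.96√(2p̄q̄)] / √(p₁q₁ + p₂q₂)}. With no removal, 44% against 29% gives 85%.

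*Assumption A: removed subjects lose half their chance of response.*
- 10% removed under ACT, 5% under usual care: 44 − 0.10 × 22 = 41.8; 29 − 0.05 × 14.5 = 28.3; difference 13.5 points, power 78%.
- Rates swapped: 44 − 0.05 × 22 = 42.9; 29 − 0.10 × 14.5 = 27.55; difference 15.35 points, power 87%.

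*Assumption B: constant chance of first response per visit; last ACT at Week 4, 8 or 12; removed subjects otherwise like the rest.* For 29% by Week 24 the chance per visit is 1 − 0.71^(1/6) = 0.0555, so 5.5%, 10.8% and 15.7% have responded by Weeks 4, 8 and 12. With no true effect, the spurious difference is the imbalance in early leaving times (29% minus the rate reached):
- Imbalance 10 points (15% against 25%): 0.10 × (29 − 15.7) = 1.3 to 0.10 × (29 − 5.5) = 2.3 points.
- Imbalance 20 points (10% against 30%): 2.7 to 4.7 points.

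The standard error is √(2 × 0.29 × 0.71 × 1.43 / 264) = 4.7 points, so type I error becomes about 6% to 8% and 9% to 17%. The arm that loses more looks worse. With a true 15-point effect:

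| Leaving early, ACT / usual care | Observed difference | Power |
|---|---|---|
| 20% / 20% | 12.7 to 13.9 | 76% to 81% |
| 15% / 25% | 15.5 to 15.6 | 89% to 91% |
| 25% / 15% | 9.8 to 12.3 | 54% to 71% |

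These rates stand for all early leaving. Item 1 would cause only part of it.

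**4. Completers-only analyses**

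If a fraction w of an arm is removed and its mean is Δ below the completers' mean, the completers' mean overstates the arm's mean by w × Δ. The treatment difference is biased by w(ACT) × Δ(ACT) − w(UC) × Δ(UC). Taking Δ = 0.5 AQLQ(S) units in both arms (assumed; this is the change that Protocol 7.3.2 calls clinically important), 25% against 15% gives 0.125 − 0.075 = 0.05, and 30% against 10% gives 0.15 − 0.05 = 0.10. Here the arm that loses more looks better, the opposite of Assumption B.

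**The case against.** The case for leaving the rule alone has substance. Exclusion criterion 12 already keeps out known poor compliers, so few subjects may be affected. The early-withdrawal visit captures ACT, AQLQ(S) and lung function, and a subject who has already responded remains a responder. If poor adherers would rarely have responded later, ending their follow-up costs the primary endpoint little. All of this stands, and it is why the primary endpoint comes last in order of exposure. It does not help the completers-only analyses, which leave out the early-withdrawal measurements.

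A reader might infer more than the documents support:

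- *That the loss is arm-related.* No compliance or withdrawal rate by arm is given. The rationale (section 2.1) speaks of adherence to guidelines and section 4.5.2 of patient empowerment, not of taking medication. Usual care may also escalate treatment. Unequal loss is a plausible risk, not a documented fact.
- *That the Per Protocol rule presupposes retention.* It does not. SAP 4.2 counts diaries over the visits completed, and SAP 4.3 runs from first to last diary date, so both work for a withdrawn subject. A subject can also fall below 80% without being judged significantly non-compliant. The sound statement is that the Per Protocol set makes removal unnecessary.
- *That the Week 12, Week 24 and Weeks 16-20-24 endpoints become on-adherence results.* They do not, because removed subjects count there as non-responders.
- *That power falls to 71%.* That figure applies the first set of rates under Assumption A to 210 per arm, already net of 20% dropout, and so counts the loss twice. On 264 enrolled per arm it is 78%; with the rates swapped it rises above the no-removal value.

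**Conclusion.** The point holds as a design weakness. A mandatory, undefined rule ends outcome collection for reasons tied to treatment-taking, in an open-label trial whose question is effectiveness and whose primary analysis is ITT. The consequence is a risk of selective loss, possibly different by arm, whose direction and size the documents do not allow anyone to state. It bears most on FEV1 and AQLQ(S), then on the diary means and by-visit models, and least on the primary endpoint.

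The illustrations rest on assumed removal rates, assumed response patterns and, for AQLQ(S), an assumed gap of 0.5. They show modest shifts when imbalance is modest, and shifts of opposite sign in the primary and completers-only analyses. They are not predictions and give no ground for claiming a specific loss of power. The 20% dropout allowance protects the number of subjects, not the balance between arms. The change is worth making because it is cheap and the missing data cannot be recovered later.

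**What to change.** Reconcile Protocol section 5.3 with sections 4.4 and 9.3.1:

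- Take non-compliance with treatment off the list of mandatory reasons to leave the study and record it as a protocol deviation.
- With the subject's continued consent, collect ACT, diary, FEV1 and AQLQ(S) on schedule to Week 24.
- Examine compliance only through the existing Per Protocol population.
- If significant non-compliance with protocol requirements stays on the list, define it.
- Align the early-withdrawal column in Protocol section 7.1 and SAP Appendix 2, the completers-only rule in SAP 7.2.2 and the handling of withdrawal visits in SAP 10.5.1.
- Report withdrawals by arm and by reason, so that any imbalance is visible.

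Treatment decisions stay with the treating doctor; nothing here proposes a treatment rule. The cost is a short protocol amendment, small consequential edits to the SAP, and some further visits with incomplete diaries. The sample size does not change.

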7.3.3. Other Endpoint (s)

- Rate of moderate/severe asthma exacerbation over the 24-week treatment period

Asthma Exacerbations

Subjects who experience worsening of symptoms should:

- increase relief medication usage for relief of symptoms
- contact the investigator or primary physician immediately and report to the clinic as soon as possible (ideally within 24 hours)
- record their symptoms, PEF and relief medication usage in their DRC, as previously instructed

- if intervention therapy is required during a treatment period, subjects may receive oral corticosteroids (40-60 mg prednisolone daily, or equivalent, for 10 days), over and above their usual asthma medication.

Exacerbations will be assessed by the physician at each scheduled visit by reviewing the DRC, as well as specific questioning on adverse events (AEs).

Exacerbations will be defined based on one or more of the following characteristics:

Definition of asthma exacerbation(s)

Moderate

A moderate asthma exacerbation is defined as a deterioration in asthma requiring treatment with an oral corticosteroid.

Individual courses of oral corticosteroids are classified as separate exacerbations only if they are administered >1 week apart. Any course started within one week of finishing the previous course is considered part of the previous exacerbation.

Severe

A severe asthma exacerbation is defined as a deterioration in asthma which requires hospital admission.

Time/date of resolution

Time/date at which the exacerbation has resolved, in the opinion of the investigator and/or subject.

Details of exacerbations must be collected in the Asthma Exacerbations page of the CRF and DRC as follows at the Visit immediately following the exacerbation:

Date of onset and resolution, daily morning PEF during the exacerbation; details of management of the exacerbation (e.g. clinic or emergency room visit, self-managed, hospital admission etc.); restriction/prevention from continuing usual activities. An exacerbation resulting in hospitalization will be recorded as a serious adverse event (SAE) in the Serious Adverse Event pages of the CRF. However, it is not only these exacerbations resulting in hospitalization which require collection as SAEs, but those that meet any of the definitions of Seriousness, listed in Section 7.4.

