9.4.3. Other Analyses

Asthma exacerbation rate will be analyzed using logistic regression as described for the primary endpoints.

Interactions between treatment and each of the covariates will be investigated in turn, with all main effects in the model regardless of their statistical significance. Any

interaction terms found to be statistically significant will be explored and if necessary results will be reported for each level of the covariate. Investigation of interactions will be confined to the primary endpoints. The effect of interactions (e.g., treatment by centre) will be assessed at the 10% level of significance.

Adverse events

The number (%) of subjects in each treatment group with treatment emergent AEs will be produced. Counts and percentages will also be presented of subjects with serious adverse events (SAEs), AEs leading to withdrawal, AEs by severity and AEs by relationship to study drug.

Other safety measures

Reason for withdrawal will be summarised.

Summary statistics for vital signs evaluations at each visit will be presented by treatment group. In addition, summary statistics for change from baseline for vital signs evaluations will be presented by treatment group.

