7.3. Exploratory Efficacy Analyses

Moderate/severe asthma exacerbations will be summarized, including number of subjects with moderate/severe exacerbations, number of moderate/severe exacerbations and characteristics of moderate/severe exacerbations. Exacerbations separated by less than 7 days will be treated as a continuation of the same exacerbation

The moderate/severe exacerbation rate will be analyzed using a generalized linear model, assuming the number of exacerbations has a negative binomial probability distribution and that its mean is related to covariate factors with a 'log link' function. The logarithm of time (year) on study will be used as an offset variable. All moderate/severe

exacerbations observed during the study, with the onset date of event from date of baseline visit to the end of study visit date or early withdrawal (from study) visit date, will be included in the analysis. Missing data due to early withdrawal from the study will not be imputed. The model will include covariates for treatment, baseline ACT total score, type of baseline controller (ICS alone vs. ICS/LABA), gender and age. The annual moderate/severe exacerbation rates and 95% confidence interval for each treatment will be presented. The rate ratio and 95% confidence interval, percent reduction in rate and 95% confidence interval and P value will also be presented.

The example SAS codes are as below:

```
proc genmod data= input_data;  
  class rndgrp blcontrol gender;  
  model no_exac = rndgrp actbl blcontrol gender age / dist=negbin  
link=log offset=logtime wald type3;  
  lsmeans rndgrp / cl diff OM exp;  
run;
```

where input_data is the name of the input dataset and no_exac is the number of moderate/severe asthma exacerbations per subject during the study. In terms of the covariates rndgrp, actbl, blcontrol, gender and age are variables for randomised treatment code, baseline ACT total score, type of baseline controller, gender and age respectively. For offset, logtime is logarithm of time (year) on study.

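### Mandatory study exit at an exacerbation, combined with the completers-only rule in SAP 7.2.2, drops most exacerbating subjects from the FEV1 and AQLQ(S) analyses

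*Protocol*

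**What the plan says.** **Exit.** Protocol 5.3 lists reasons that oblige discontinuation from the study itself, not only from treatment. Item 5 reads "Subjects experience a protocol-defined asthma exacerbation". Item 4, "In the investigator's opinion, it is in the subject's best interest", is a separate reason. The only definition of an exacerbation is in Protocol 7.3.3: "A moderate asthma exacerbation is defined as a deterioration in asthma requiring treatment with an oral corticosteroid", while a severe one leads to hospital admission.

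**FEV1 and AQLQ(S).** SAP 7.2.2 restricts both changes from baseline to study completers and computes them from baseline and Visit 6. Protocol 5.4 and SAP 10.5.1 define completion as attending every visit. The Time and Events Table (Protocol 7.1) puts both measures in the column shared by Visit 6 and early withdrawal, and Protocol 5.3 requires the early-discontinuation procedures at exit. SAP 10.5.1 uses withdrawal data by default but yields to any more specific rule, and SAP 7.2.2 is such a rule.

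**Exacerbations.** Protocol 7.3.3 allows treatment in the study ("if intervention therapy is required during a treatment period, subjects may receive oral corticosteroids") and gives a counting rule: "Individual courses of oral corticosteroids are classified as separate exacerbations only if they are administered >1 week apart". Protocol 9.4.3 says "Asthma exacerbation rate will be analyzed using logistic regression as described for the primary endpoints". SAP 7.3 instead fits a negative binomial model in which "no_exac is the number of moderate/severe asthma exacerbations per subject during the study". It uses log time on study as offset, counts events up to the early-withdrawal visit, and adds that "Exacerbations separated by less than 7 days will be treated as a continuation of the same exacerbation".

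**The concern.** A subject who exacerbates before the last visit has to leave, is therefore not a completer, and is left out of the FEV1 and AQLQ(S) analyses even if both were measured at exit. The reason for being missing is a bad asthma outcome, and asthma outcome is what these endpoints measure. Each arm is then described mainly by subjects who did not exacerbate. If the arms have the same exacerbation rate and the same deficit, the distortion cancels in the comparison; if the rates differ, it does not. Should ACT guidance reduce exacerbations, usual care loses more of its worst subjects and looks better than it is.

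A smaller question concerns the exploratory endpoint. The plan has rules for separating repeat events and a count model, but exit at the first event leaves almost no repeat events to count.

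**Working it through.** **Plan's own figure.** 35 evaluable subjects per centre / (1 − 0.20 dropout) = 43.75, so 44; 44 × 12 centres = 528 (Protocol 9.2.1). This point does not dispute it. The documents give no exacerbation rate, so every rate and deficit below is an assumption.

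**Step 1: who is lost.** With a constant annual rate r, the share with a first event by week w is 1 − exp(−r × w/52). A subject with a first event before Week 20 cannot complete all visits. A subject with a first event after Week 20 is lost only if exit comes before Visit 6. (The ±1-week visit windows are ignored.)

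| Assumed r per year | By Week 20 | By Week 24 | Exits of 528 | Week 20 / Week 24 |
|---|---|---|---|---|
| 0.2 | 0.074 | 0.088 | 39–47 | 84% |
| 0.3 | 0.109 | 0.129 | 58–68 | 84% |
| 0.4 | 0.143 | 0.169 | 75–89 | 85% |
| 0.6 | 0.206 | 0.242 | 109–128 | 85% |

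If rates vary between subjects (gamma, dispersion 1), the share is 1 − 1/(1 + r × w/52). At 0.2 this gives 0.0714/0.0845 = 85%; at 0.6, 0.1875/0.2169 = 86%. The share of exacerbating subjects removed is therefore about 84% to 86% across these assumptions, and higher if some late events also lead to exit before Visit 6.

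**Step 2: bias in FEV1 and AQLQ(S).** Let the deficit be how much worse the change from baseline is, on average, in an exacerbating subject than in another subject of the same arm. Dropping a share s of the arm raises its mean by about s × deficit. The between-arm bias is the difference in s times the deficit.

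- At 0.2 (ACT) versus 0.4 (usual care), the difference in s is 0.069 by Week 20 and 0.080 by Week 24.
- AQLQ(S), deficit 0.5: 0.034 to 0.040; deficit 1.0: 0.069 to 0.080. Protocol 7.3.2 treats a change above 0.5 as important.
- FEV1, deficit 100 mL: 7 to 8 mL; deficit 200 mL: 14 to 16 mL.
- At 0.3 versus 0.4, the difference in s is 0.034 to 0.039, which gives 0.017 to 0.039 AQLQ(S) points or 3 to 8 mL.

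In each case usual care gains, so the bias is against ACT guidance.

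**Step 3: exacerbation rate.** Simulation with 2 million subjects per setting, exit at the next 4-weekly visit, and a second event counted only if it starts at least 17 days after the first (10-day course plus 1 week). At 0.2 to 0.6 per year, two separate events before exit are recorded in 0.06 to 0.46 of 528 subjects (constant rate) or 0.10 to 0.74 (dispersion 1), so on average in fewer than one subject. Events per person-year:

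| Assumed r | Variation between subjects | With exit | Full follow-up | Change |
|---|---|---|---|---|
| 0.2 | none | 0.199 | 0.199 | none |
| 0.4 | none | 0.395 | 0.393 | under 1% |
| 0.2 | dispersion 1 | 0.191 | 0.197 | 3% lower |
| 0.4 | dispersion 1 | 0.366 | 0.388 | 6% lower |
| 0.6 | dispersion 1 | 0.525 | 0.570 | 8% lower |

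**The case against.** **The plan contradicts itself on exacerbations.** A reader might infer that Protocol 5.3 cannot be squared with Protocol 7.3.3 and SAP 7.3. The documents do not support that. An oral corticosteroid can be given for the event that triggers exit, its details can be recorded at the early-withdrawal visit, and the event still counts. The one-week rule can still classify courses that fall between two visits. Protocol 9.4.3 analyses occurrence, which suits exit at the first event, and SAP 7.3 provides for early withdrawal through its offset and its end date for counting.

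**The exacerbation analysis is badly biased.** Compared with full follow-up, 3.5% to 10% of separate events go unrecorded at a constant rate, and 7% to 17% with dispersion 1. These are raw counts. Person-time falls as well, and the offset allows for that, so the rate moves only as shown in Step 3.

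**The primary endpoint is at risk.** A response at any one visit is enough, so early exit costs little. Under an assumed no-change model with visit-to-visit noise, the between-arm effect at 0.2 versus 0.4 per year is about 0.7 percentage point, against the planned 15. In addition, three sensitivity endpoints in SAP 7.1.3 already count missing ACT scores as non-response.

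**The remaining concern is small.** It touches two of the eight secondary endpoints in the SAP, the bias is well below 0.5 AQLQ(S) points, and it is conservative if ACT guidance works. Halving the exacerbation rate is an assumption that no document supports. The exclusion of subjects with repeated severe exacerbations or recent oral corticosteroids (Protocol 5.2) argues against the higher rates. All of this is fair and limits the weight of the point. It does not justify leaving scheduled measurements out of the analysis because the subject did badly.

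**Conclusion.** The point holds for FEV1 and AQLQ(S). That exacerbating subjects who leave early are excluded follows from the text alone. That they make up about 84% to 86% of all exacerbating subjects depends only weakly on the assumed rate. The size of the bias depends on assumed rates and deficits: about 0.03 to 0.08 AQLQ(S) points or 7 to 16 mL at 0.2 versus 0.4 per year, less if the rates are closer, and none from this source if rates and deficits are equal. If ACT guidance lowers exacerbations, the bias is against it; if it raises them, the direction reverses.

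For the exploratory endpoint the matter is mainly one of description. The SAP 7.3 model in effect estimates a first-event rate, which is essentially unchanged at a constant rate and about 3% to 8% lower with dispersion 1. The documents do not support a claim of outright contradiction, of a seriously biased exacerbation rate, or of a threat to the primary endpoint.

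**What to change.** **Main change (SAP 7.2.2).** Replace the completers-only rule so that every subject with a Visit 6 or early-withdrawal FEV1 or AQLQ(S) value is included, and show the results with and without the early-withdrawal values. The cost is a short SAP edit and one extra set of displays; no new measurement is needed. The drawback is that early-withdrawal values come before Week 24 and may reflect the acute event, so including them could overstate the lasting deficit. Reporting both shows how far the conclusion depends on this.

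**If mandatory exit stays (SAP 7.3).** Describe the result as a first-exacerbation rate. This costs one sentence.

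**Optional, if an amendment is feasible (Protocol 5.3).** Remove item 5 as a mandatory reason to leave the study, and continue the scheduled visits to Week 24 in subjects who agree. The trial provides no study drug that would have to be stopped (Protocol 6.1), and item 4 still allows exit in the subject's best interest. This is a more debatable design change. It needs ethics committee review and possibly renewed consent (Protocol 10.2), and some later ACT scores would then follow a corticosteroid course. SAP 6.1 refers to a March 2018 drug dictionary, so the trial may already have been well advanced; the documents do not settle this. The SAP edit is worth making either way.
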